5.1.3 Study Follow-Up

Follow-Up Visit (V9) (LCIG Subjects not Continuing on Commercial Product)

For subjects who are not continuing on LCIG (through commercial sources in countries where LCIG is approved and marketed), the PEG-J tube will be removed following the End of Study activities. A follow-up clinic visit will occur approximately one week later.

Commercial Transition Visits (LCIG Subjects Continuing on Commercial Product)

Study subjects in the LCIG group who complete participation in the study and for whom continuation of treatment with LCIG is judged appropriate by the Investigator will continue to receive LCIG until transition to commercial product is coordinated with the Sponsor's commercial affiliate.

Additional visits every 12 weeks from Week 26 will be schedule to monitor subject safety and allow for drug resupply until the subject transfer to commercial LCIG. Refer to [Table 3](#) of Section [5.3.1.1](#) for list of assessments. Drug resupply visits will also occur at 6 week intervals between the every 12 week safety assessments.

Upon transfer of subjects to commercial LCIG the monitoring of such therapy will be the responsibility of the subject's personal physician. All necessary support will be provided by the Sponsor's local representative. Follow-up care in these circumstances will be based on the judgment of the subject's personal physician and no formal collection of data will be conducted except for regular ADR-reporting in accordance with local instructions.

OMT Subjects

Study subjects in the OMT group who complete participation in the study are eligible to transition to commercial LCIG after end of study procedures if judged appropriate by their personal physician. This transition is not study related.

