5.3 Efficacy and Safety Assessments/Variables

5.3.1 Efficacy and Safety Measurements Assessed and Flow Chart

After a subject has signed the Informed Consent, the study activities described in [Table 3](#) will be completed. Subject visit days should ideally match the target clinic visit days. Every attempt should be made to bring the subject back on the target visit day. A ± 3 day visit window will be allowed as necessary beginning with the Week 2 visit and a ± 7 day visit window will be allowed as necessary beginning with the Week 6 visit. All attempts should be made to return the subject to the planned visit schedule (e.g., if the subject is two days late for a Study Visit, the scheduling of the next visit date should be based on the original planned visit date). All scheduled visits are calculated based on Study Day 1 (NJ and/ or PEG-J Placement Day for subjects randomized to LCIG and day after randomization for subjects randomized to OMT).

Table 3. Study Activities

Study Day (End of Week)	OMT/LCIG				Titration Visits	OMT/LCIG				LCIG Wk 27 FU ^a	LCIG Transition to Commercial Visits ^b
	V1 Screening Wk -8/-4	V2 Screening Wk -1	V3 Randomization	V4 NJ/PEG-J Placement DI		Wk 2	Wk 6	Wk 12	Wk 17		
Visit Number for OMT/LCIG	V1	V2 ^c (Optional)	V3	V4 ^d	V5	V6	V7		V8	V9	Every 6 and 12 Weeks
Informed Consent ^e	X										
Medical/Neurological/PD History ^f	X										
Concomitant Medication (including anti-PD and NMS medications)	X	X	X	X	X	X	X		X	X	
Anti-PD Medication History	X										
NMS Medication History ^g	X										
MMSE (Mini-Mental State Examination)	X										
Sleep Attacks Questionnaire	X	X	X		X	X	X		X	X	
Physical Examination ^h	X	X	X	X	X	X	X		X	X	
Neurological Exam	X	X	X		X	X	X		X	X	
Dermatological Exam ^h	X								X		
GI Exam ^h	X										
NJ or PEG-J decision	X										
Nasojejunal Tube Placement/Titration ⁱ (Optional)				X							
PEG-J Placement Procedure ^j				X							

Table 3. Study Activities (Continued)

Study Day (End of Week)	OMT/LCIG			LCIG V4 NJ/PEG-J Placement D1	Titration Visits	OMT/LCIG				LCIG	Transition to Commercial Visits ^b	
	V1 Screening Wk -8/-4	V2 Screening Wk -1	V3 Randomization			Wk 2	Wk 6	Wk 12	Wk 17			Wk 22
Radiological Check of Tube Placement ^j				X								
PEG-J Site (Stoma) Check				X ^k	X	X	X		X		X	
Vital Signs ^l /Weight	X		X	X	X	X	X		X		X	X
Height ^m	X											
ECG	X						X		X			
Clinical Labs ⁿ (+ urinalysis) ⁿ	X	X	X ⁿ				X		X			
Urine Drug/Alcohol Screen	X											

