- t. PEG-J removal will be complete 1 week before follow up visit.
- u. At Week 27 follow up visit LCIG cassettes return only.

Note: All applicable clinical, safety, health outcome and cognition assessments will be administered only by individuals qualified by the Sponsor.

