6.4 Analysis by Planned Visit

A midpoint convention will be used to assign all observations to a planned visit based on the Study Day of the observation. If there are multiple observations on the same day, the average will be taken and considered the observation for the day. If more than one observation is assigned to a planned visit, the last observation will be selected and considered the observation for the planned visit.

The following Study Day windows will be used to assign efficacy and health outcome assessments to planned study visits during 26-week randomized treatment period.

Table 1. Analysis Windows for Efficacy Variables

Assessment	Planned Visit	Nominal Study Day	Study Day Range ^a
NMSS, PDSS-2, PDQ-8, PAS, GDS-15, UPDRS and King's PD Pain Scale	Baseline		≤ date of randomization
	Week 6	42	2 – 63
	Week 12	84	64 – 133
	Week 26	182	134 – 222
CGI-C and PGIC	Week 26	182	≥ 2

a. For subjects in LCIG group, all post-baseline assessments must also be after start of LCIG infusion through PEG-J and no more than 1 day after the date of the last LCIG infusion in the 26-week Treatment Period.

The following Study Day windows will be used to assign safety assessments to planned study visits.

Table 2. Analysis Windows for Safety Variables During the 26-Week Treatment Period

Assessment	Planned Visit	Nominal Study Day	Study Day Range ^a
Vital signs and weight	Baseline		≤ date of randomization
	Week 2	14	2 – 28
	Week 6	42	29 – 63
	Week 12	84	64 – 133
	Week 26	182	134 – 186
	Week 27 FU ^b	189	187 – 301
Clinical labs and Electrocardiograms	Baseline		≤ date of randomization
	Week 12	84	2 – 133
	Week 26	182	> 133
Special labs	Baseline		≤ date of randomization
	Week 12	84	2 – 133
	Week 26	182	134 – 231

- a. For subjects in LCIG group, all post-baseline assessments must also be no more than 1 day after the final PEG-J removal for subjects who have their study device removed after their last infusion of Study M12-927 LCIG.
- b. Applicable only to LCIG subjects who will not transition to commercial LCIG and have study device removed.

The following Study Day windows for Extension Period will be used to assign safety assessments to planned study visits for LCIG subject entering Extension Period.

Table 3. Analysis Windows for Safety Variables During the Extension/Transition Period for the LCIG Group

Assessment	Planned Visit	Nominal Study Day	Study Day Range ^a

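### The Week 26 vital-sign and weight window in SAP Table 2 closes three days before the last permitted Week 26 visit day, and the table's Week 27 row excludes the follow-up visit it is named for

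*SAP*

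**What the plan says.** Protocol 5.3.1 sets the visit clock: "All scheduled visits are calculated based on Study Day 1". Study Day 1 is the day of NJ or PEG-J placement for LCIG and the day after randomization for OMT. The tolerance is plus or minus 7 days for the later visits: "7 day visit window will be allowed as necessary beginning with the Week 6 visit".

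SAP 6.4 gives the assignment rule: "A midpoint convention will be used to assign all observations to a planned visit based on the Study Day of the observation". For vital signs and weight, Table 2 then prints Days 134 to 186 for Week 26 (nominal Day 182) and Days 187 to 301 for Week 27 FU (nominal Day 189). Two footnotes matter:

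- Footnote a is attached to the day-range column, so it covers every row. It concerns the LCIG arm only and requires that "all post-baseline assessments must also be no more than 1 day after the final PEG-J removal for subjects who have their study device removed".
- Footnote b is attached to the Week 27 FU row: "Applicable only to LCIG subjects who will not transition to commercial LCIG and have study device removed".

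On the follow-up itself, Protocol 5.1.3 says of the time after tube removal: "A follow-up clinic visit will occur approximately one week later". A footnote to Protocol Table 3 agrees: "PEG-J removal will be complete 1 week before follow up visit". The protocol synopsis states that OMT subjects have no follow-up visit.

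**The concern.** There are two faults in the same part of Table 2.

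First, the Week 26 upper limit comes from a midpoint with Week 27, but most subjects have no Week 27 visit. A subject seen late but within tolerance can fall past the limit and into a row that footnote b closes to that subject.

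Second, the Week 27 row exists for subjects whose device has been removed. Footnote a discards their readings from the second day after removal onward, which includes the scheduled follow-up.

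What is at stake is limited. SAP 10.4.1 compares the arms by ANOVA on change in vital signs and weight at each planned visit. A permitted late reading would drop out of that Week 26 comparison, while other measures taken at the same visit would still count as Week 26. Weight loss is an adverse event of special interest for this product, so the by-visit weight table will be read.

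**Working it through.** **Reproducing the printed limits.** The nominal days for vital signs and weight in Table 2 are 14, 42, 84, 182 and 189. The midpoints are:

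- (14 + 42)/2 = 28, printed 28
- (42 + 84)/2 = 63, printed 63
- (84 + 182)/2 = 133, printed 133
- (182 + 189)/2 = 185.5, printed 186 (rounded up)

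Day 186 is therefore the SAP's own rule applied to Weeks 26 and 27, not an arithmetic slip.

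**Comparison with the permitted visit days.** The Week 26 visit is allowed from 182 − 7 = 175 to 182 + 7 = 189, which is 15 days. Days 187, 188 and 189 lie beyond 186, so 3 of the 15 days, or visits 5, 6 or 7 days late, are outside the Week 26 row.

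**Where a reading on Days 187 to 189 goes:**

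| Subject | Row for the reading |
|---|---|
| OMT | None: footnote b closes Week 27 FU |
| LCIG, continuing or transitioning | None: footnote b closes Week 27 FU |
| LCIG, device removed | Week 27 FU, although it is a Week 26 reading |

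Tables 3 and 4 do not catch these readings. By SAP 6.2 the OMT treatment period runs to the final visit of the 26-week period, so a Day 188 visit still belongs to it. For LCIG, Table 3 treats readings up to the last 26-week visit as baseline, not as a post-baseline visit.

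**Other measures at the same visit.** The Week 26 upper limit is Day 222 for the main efficacy scales (Table 1) and Day 231 for special labs (Table 2). Clinical labs and ECG have no upper limit (any day after 133). All of these include Day 189; only vital signs and weight do not.

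**Footnote a against the follow-up visit.** The limit is removal + 1 day and the visit is at about removal + 7 days, so the visit is about 7 − 1 = 6 days too late. With removal on Day 182, the limit is Day 183 and the visit falls on Day 189. With removal on Day 189, the limit is Day 190 and the visit falls on Day 196. Under footnotes a and b together, the Week 27 row can hold late Week 26 or removal-day readings but not the scheduled follow-up.

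**Summaries that do not use these windows.** The final value (SAP 6.3), the minimum and maximum (SAP 10.4.1) and potentially clinically significant values (SAP 10.4.3) are defined over the treatment period. Weight AESIs (SAP 10.2.3) are defined by MedDRA terms.

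**The case against.** The best counter-reading is that SAP 6.4 assigns every observation to a planned visit. A subject with no Week 27 visit has no 182/189 midpoint, so a Day 187 to 189 reading would belong to Week 26 by default. Likewise, a row reserved for subjects with the device removed shows that their follow-up readings were meant to be kept, so footnote a merely lacks an exception. Both are plausible guesses at intent, but neither is what is printed. Table 2 gives a single range, 134 to 186, and footnote a covers all post-baseline assessments. A programmer following the text would exclude the readings.

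The point about size stands. Protocol 5.3.1 says: "Every attempt should be made to bring the subject back on the target visit day". Late visits may be few, and a late reading still enters the between-arm comparison as the final value. The Week 27 row is LCIG-only, so no between-arm test depends on it.

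One qualification to the day count also stands. The synopsis counts LCIG visits from PEG-J placement, whereas Protocol 5.3.1 and the SAP count from the first NJ or PEG-J placement. With an NJ phase of up to 7 days, a visit on target by the synopsis clock could fall as late as SAP Day 182 + 7 = 189. This can only move visits to later Study Days, so it does not remove the fault.

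On the remedy, Day 189 would be enough under the Protocol 5.3.1 clock. Because the last reading in a window is the one used, a longer window could let an unscheduled later reading replace the Week 26 one. That is a fair caution, and the period-end statement in the fix is there for it.

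**Conclusion.** Both faults hold as the SAP is written. The Week 26 vital-sign and weight row misses 3 of the 15 permitted visit days, and the Week 27 row excludes its own visit by about 6 days. The first result rests on the Protocol 5.3.1 visit clock, under which only visits 5 to 7 days late are affected. The second rests on the follow-up taking place about a week after removal, as scheduled; only a very early follow-up could meet the footnote a limit.

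The number of subjects affected cannot be derived, because the documents give no spread of visit days. The consequence is confined to the by-visit vital-sign and weight summaries and the Week 26 ANOVA on them. No efficacy, power or alpha figure changes. This is a minor error that is worth correcting because correction is nearly free.

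**What to change.** In SAP Table 2:

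1. Set the Week 26 window for vital signs and weight to Days 134 to 222, matching Table 1. Keep footnote a for this row, so that the scheduled post-removal follow-up stays out of Week 26.
2. State that readings after the end of the 26-week period, as defined in SAP 6.2, stay in Tables 3 and 4. This matters for OMT subjects who enter the extension, whose first LCIG visits could otherwise fall before Day 222. For LCIG subjects in transition, the first 12-week safety visit is at about 182 + 84 = Day 266, or Day 259 if 7 days early, so the wider window takes in no scheduled transition safety reading.
3. For Week 27 FU, preferably assign the reading by visit (V9), exempt it from footnote a and summarise it descriptively for LCIG only. Study Day alone cannot separate a Week 26 visit on Day 189 from a follow-up with nominal Day 189. Subjects who discontinue early also have this follow-up, on any Study Day, so a label such as post-removal follow-up would be more accurate. The alternative is to delete the row, which leaves those readings without a by-visit summary.

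The cost is one window limit, one clarifying sentence, and either one assignment rule with a footnote exemption or one deleted row, all before database lock. Neither the protocol nor data collection changes.

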4.2 Design Diagram

This is a Phase 3b, open-label, randomized multicenter 26-week study comparing LCIG to OMT for the treatment of non-motor symptoms in subjects with advanced Parkinson's disease.

The study will consist of three sequential parts:

Part 1: Screening period. The screening period will consist of three visits, Visit 1 (V1), Visit 2 ([V2] [optional]) and the Randomization Visit (V3) in which the subject will be assessed to determine eligibility. The duration of the Screening Period can be between 30 – 67 days to accommodate the required procedures, training and collection of diaries, and to allow for stabilization of anti-PD medications and medications to treat NMS. All anti-PD medications and medications to treat NMS are required to be stable for a minimum of 30 days prior to randomization.

Part 2: Treatment period. Those subjects randomized to OMT at the end of V3 will remain on their current optimized regimen. The day after randomization will be considered Day 1 of their treatment period and subjects will have study visits at the end of Weeks 2, 6, 12, and 26. All subjects randomized to the LCIG group should have all anti-PD medications, with the exception of levodopa formulations, tapered off within 14 days after randomization. Optional nasojujunal and/or percutaneous endoscopic gastrostomy with a jejunal tube (PEG-J) placement will then be placed. After that, the subject may begin initiation and titration of LCIG infusion to be adjusted to obtain the optimal clinical response in 14 days. The day of initial NJ or PEG-J placement will be considered Day 1 for subjects in the LCIG group. Study visits happen at the end of Weeks 2, 6, 12, and 26.

Part 3: Extension Period. Subjects in the United States or South Korea from both treatment arms who complete the 26 week study may continue into the Extension Period of the study. South Korea subjects in the LCIG arm will have study drug dispensation every 4 weeks and will have study visits every 6 months. South Korea subjects from the OMT arm will undergo the NJ (optional) and PEG-J procedures, titration, plus have visits at 2 weeks, 6 weeks, 3 months and 6 months post NJ or PEG-J. Subjects will then continue to receive study drug every 4 weeks and will have study visits every 6 months until Duodopa is commercially available.

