United States subjects in LCIG arm will continue to have study drug dispensation every 4 weeks and will have study visits at 3 and 6 months, or the day prior to transition to commercial if that happens before the scheduled study visits. United States subjects from the OMT arm will undergo the NJ (optional) and PEG-J procedures, titration, plus have visits at 2 weeks, 6 weeks, 3 months and 6 months post NJ or PEG-J, or the day prior to transition to commercial if that happens before the scheduled study visits. Subjects will receive study drug every 4 weeks. The Extension Period will last for a maximum of 6 months to allow for continuity of care while the transition to commercially available drug occurs.

Part 4: Follow-up period. For subjects who elect to discontinue LCIG treatment at any time during the study, the PEG-J tube will be removed following the End of Study activities. A follow-up clinic visit will occur approximately 1 week later. For study subjects who complete participation in the study and will continue to receive LCIG, subjects will return every 6 weeks to return used LCIG cassettes and be dispensed cassettes. Additional visits every 12 weeks from Week 26 will be scheduled to monitor subject safety and allow for drug resupply until the subject transfers to commercial LCIG.

Figure 1. Study Design Schematic (All Countries Except for United States and South Korea)

[figure not shown]
[figure not shown]
[figure not shown]

Figure 2. Study Design Schematic (United States)

Extension Period:

OMT Subjects

LCIG Subjects

[figure not shown]
[figure not shown]
[figure not shown]

Figure 3. Study Design Schematic (South Korea)

[figure not shown]

Extension Period:

OMT Subjects

LCIG Subjects

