Vital signs and weight, Clinical labs ^a , Electrocardiograms ^a , and special labs	Baseline ^b		≤ date of last visit in 26-week randomized treatment period for subjects randomized to LCIG group.
	Month 3 ^c	84	1 – 126
	Month 6	168	127 – 200
	Every 3 months following until subjects' transition to commercial LCIG	Previous + 84	Previous lower bound + 84 through previous upper bound + 84

- a. Clinical labs and Electrocardiograms will not be collected during the Transition Period.
- b. Baseline refers the baseline of Extension Period. All days refer to study day in Extension Period. All post-baseline assessments must also be no more than 1 day after the final PEG-J removal for subjects who have their study device removed after their last infusion of Study M12-927 LCIG.
- c. Applicable only to US subjects.

The following Study Day windows for Extension Period will be used to assign safety assessments to planned study visits for OMT subject entering Extension Period.

Table 4. Analysis Windows for Safety Variables During the Extension/Transition Period for the OMT Group

Assessment	Planned Visit	Nominal Study Day	Study Day Range ^a
Vital signs and weight,	Baseline ^a		< date of NJ/PEG-J placement for subjects randomized to OMT group and entering Extension Period
	Week 2	14	2 – 28
	Week 6	42	29 – 63
	Month 3	84	64 – 126
	Month 6	168	127 – 200
	Every 3 months following until subjects' transition to commercial LCIG ^c	Previous + 64	Previous lower bound + 84 through previous upper bound + 84
Clinical labs ^b , Electrocardiograms ^b , and special labs	Baseline ^a		< date of NJ/PEG-J placement for subjects randomized to OMT group and entering Extension Period
	Month 3	84	2 – 126
	Month 6	168	127 – 252
	Every 3 months following until subjects' transition to commercial	Previous + 168	Previous lower bound + 168 through previous upper bound + 168

a. Baseline refers the baseline of Extension Period. All days refer to study day in Extension Period. All post-baseline assessments must also be no more than 1 day after the final PEG-J removal for subjects who have their study device removed after their last infusion of Study M12-927 LCIG.

b. Clinical labs and Electrocardiograms will not be collected during the Transition Period.

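### After Month 6, the repeat visit windows in SAP Tables 3 and 4 leave calendar days in no window, so some extension values would drop out of the by-visit mean-change tables

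*SAP*

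**What the plan says.** SAP section 6.4 opens with the assignment rule: "A midpoint convention will be used to assign all observations to a planned visit based on the Study Day of the observation". Tables 3 and 4 apply it to the Extension/Transition Period.

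- **Table 3** (LCIG arm; vital signs, weight, laboratory tests, ECG, special laboratory tests). Month 3 has nominal Day 84 and Days 1–126, with the footnote "Applicable only to US subjects". Month 6 has nominal Day 168 and Days 127–200. After that the nominal day advances by 84 and the range is "Previous lower bound + 84 through previous upper bound + 84".
- **Table 4, vital signs and weight** (OMT subjects entering the extension). Month 6 is again nominal Day 168, Days 127–200. The range moves by 84, but the nominal day in the same row advances by 64.
- **Table 4, laboratory tests, ECG and special laboratory tests.** Month 6 is nominal Day 168, Days 127–252. The nominal day then advances by 168 and the range is "Previous lower bound + 168 through previous upper bound + 168". The row is labelled "Every 3 months following until subjects' transition to commercial".

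SAP section 4.2 gives the schedules these windows must serve. South Korea subjects who cross over from OMT "will have study visits every 6 months until Duodopa is commercially available", and South Korea LCIG-arm subjects are also seen every 6 months. For the United States, "The Extension Period will last for a maximum of 6 months". Subjects who complete the study and await commercial product have safety visits every 12 weeks from Week 26.

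SAP sections 10.3.1, 10.4.1 and 10.5.1 call for mean change to each planned visit in this period.

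**The concern.** Adding a constant to both bounds of a window gives adjoining windows only if the window is as wide as the constant. Here a 74-day window (127–200) is moved by 84 days, and a 126-day window (127–252) is moved by 168 days. Both rows therefore leave holes, although the section says that all observations are assigned. Within Table 4, the nominal day and the range of one row move by different amounts, and a row with a 168-day step carries a three-month label.

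A programmer who follows the tables literally must leave a value that falls in a hole out of the by-visit tables. The alternative is to improvise a rule the SAP does not contain. The repeat windows will be used, because the South Korea extension is open-ended. OMT subjects receive study LCIG only in the extension, so these tables are their only by-visit LCIG summaries.

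**Working it through.** **1. Reproduce the stated bounds.** The upper bound should be (nominal day + next nominal day) / 2. Inputs are the nominal days in Tables 3 and 4.

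- Month 3: (84 + 168)/2 = 126. Matches.
- Month 6, Table 4 laboratory tests: (168 + 336)/2 = 252. Matches.
- Month 6, Table 3 and Table 4 vital signs, next nominal day 168 + 84 = 252: (168 + 252)/2 = 210. The tables say 200.
- Same bound with the 64-day step, next nominal day 168 + 64 = 232: (168 + 232)/2 = 200. Matches exactly.

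So 200 fits a 64-day step, while the range is moved by 84.

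**2. Roll the windows forward.**

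- Table 3 and Table 4 vital signs (+84): 127–200, 211–284, 295–368, 379–452, 463–536, 547–620. Uncovered: Days 201–210, 285–294, 369–378, 453–462, 537–546. That is 84 − 74 = 10 days per 84-day cycle (11.9% of days).
- Table 4 laboratory tests, ECG and special laboratory tests (+168): 127–252, 295–420, 463–588, 631–756. Uncovered: Days 253–294, 421–462, 589–630. That is 168 − 126 = 42 days per 168-day cycle (25% of days).

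**3. Nominal days in the Table 4 vital-signs row (+64).** These run 232, 296, 360, against windows 211–284, 295–368, 379–452. From the third repeat the nominal day lies outside its own window.

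**4. Which scheduled visits are exposed?** Assume that the ±7-day visit tolerance in protocol section 5.3.1 carries over to the extension.

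- 84-day spacing, Table 3: 252 ± 7 lies in 211–284 and 336 ± 7 in 295–368. None lost.
- 168-day spacing, Table 4 laboratory tests: 336, 504 and 672, each ± 7, lie in 295–420, 463–588 and 631–756. None lost.
- 6 months counted as 26 weeks (182 days; an assumption, since the documents do not define it), Table 4 laboratory tests: 364, 546 and 728, each ± 7, all lie in a window. None lost.
- The same 26-week counting, Table 3 and Table 4 vital signs: 364 ± 7 is 357–371, and Days 369–371 are uncovered. 546 ± 7 is 539–553, and Days 539–546, including the target day, are uncovered. Day 728 lands in 715–788, whose Table 3 nominal day is 756 rather than 672.

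**5. A related hole in Table 3.** The first Transition visit comes 12 weeks (84 days) after Week 26, which belongs in Days 1–126. The footnote reserves that window for United States subjects, so elsewhere the visit has no window as written.

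**The case against.** The strongest reply accepts the arithmetic and disputes its consequence. Most of that reply stands.

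- A reader might infer from 12% and 25% that those fractions of the extension safety data are lost. The documents do not support this. The percentages are shares of calendar days, and the holes lie between planned visits. The 25% hole catches no on-schedule laboratory or ECG visit in the checks above.
- A reader might also infer that the main LCIG safety record of the crossover subjects is damaged. It is not. Their first six months are covered without a break (Days 2–28, 29–63, 64–126, 127–200; laboratory tests 2–126, 127–252). The United States extension stops at 6 months. Extension adverse events are defined in SAP section 10.2 without these windows. SAP section 6.3 takes the final extension value as the last one recorded, whatever its window. Minimum and maximum changes are reported separately from the by-visit means. Counts and listings of potentially clinically significant values (sections 10.3.3, 10.4.3 and 10.5.2) need only a qualifying value in the period.
- The 168-day step is not an error in itself. It fits the 6-monthly South Korea schedule in Appendix B, and 252 is the correct midpoint. The faults in that row are its label and the moving of a 126-day window by 168 days.
- The 64-day step sits in the nominal-day column and assigns nothing. Its harm is a wrong nominal day and, apparently, the bound of 200.

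What the reply does not remove is the conflict between the opening sentence of section 6.4 and the windows that follow it.

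**Conclusion.** The point holds and is minor. The repeat windows after Month 6 are wrong as written: they leave 10 of every 84 calendar days uncovered for Table 3 and Table 4 vital signs, and 42 of every 168 for Table 4 laboratory tests, ECG and special laboratory tests.

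The effect is limited to by-visit mean-change tables in the Extension/Transition Period after Month 6, mainly for South Korea extension subjects and Transition subjects. The values at risk are unscheduled, late or discontinuation-visit values. If 6 months is counted as 26 weeks, some scheduled vital signs and Table 3 values are also at risk, such as those on Day 546. The number of values cannot be derived from the documents. The randomized 26-week comparison is untouched. The gap arithmetic needs no assumption; the statements about scheduled visits rest on the 26-week reading and on the ±7-day tolerance carrying over.

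**What to change.** Give each row one step for both nominal day and range, match it to the visit schedule, and make the windows contiguous at the midpoints.

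- **Table 3 (84-day step):** Month 6 = 127–210, then 211–294, 295–378, 379–462.
- **Table 4 laboratory tests, ECG and special laboratory tests (168-day step):** relabel as every 6 months; 127–252, then 253–420, 421–588, 589–756.
- **Table 4 vital signs and weight:** remove the 64-day step. Preferably use the 168-day step, which matches the 6-monthly visits in Appendix B (127–252, then 253–420), and relabel the row. If an 84-day step is kept, use 127–210, then 211–294; this creates windows with no scheduled visit for crossover subjects.
- **Table 3, Month 3 footnote:** reconcile the restriction to United States subjects with the 12-week Transition visits in section 4.2.
- **State how many days 6 months means.** The 84-day row in Table 3 also serves the 6-monthly South Korea LCIG visits. On a 26-week count, a Day 546 visit held one day late would still fall in 547–630, labelled Day 588 rather than Day 504.

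The cost is a few edits to SAP tables and the matching programming specification. No new data are needed and the primary analysis does not change.
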